## **12. Sample size calculation**

The sample size calculation was based on detecting a difference between vildagliptin and dapagliflozin in the AUC of glucagon level during the 300 min after mixed meal ingestion after 2 weeks of treatment. Previous studies on the effect of vildagliptin (3) and dapagliflozin (4) showed a reduction of glucagon by vildagliptin and an increase of glucagon by dapagliflozin. Based on these data and expecting similar variation in the data in the population studied here, a power analysis aiming at showing a 30% difference in glucagon levels by the two drugs with 90% sensitivity results in requirement of 24 subjects when doing paired analysis. To allow for even more safe statistics and allow for discontinuation, we will recruit four additional subjects; hence we aim at including 28 patients in the study.

### **13. Statistical evaluation**

The variables will be analyzed using a 2-sided paired test. The Completers population alone will be used.

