## Figure of Study Design

Each patient will therefore receive two treatments in a randomized design:

Vildagliptin 50 mg twice daily (BID) during weeks 0-2 and Dapagliflozin 10 mg once daily (QD) during weeks 6-8 or

Dapagliflozin 10 mg QD during weeks 0-2 and Vildagliptin 50 mg BID during weeks 6-8

The study medication will not be blinded.

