## 9. Data management and safety registration

**Registration.** The data are recorded in case and visit notes (hospital records) and entered in the CRF containing demographic and medical information, laboratory data, electrocardiograms, and the specific study-related results of any other tests or assessments. Specific worksheets will be the source documents for the variables derived from the mixed meal test. These will be stored in the CRF. A certified study monitor will regularly inspect the CRFs to ensure accuracy with source data.

**Safety.** At first visit, study subjects are informed of the characteristic symptoms of acute pancreatitis (persistent and abdominal pain). Adverse events are acute pancreatitis and hypoglycemia and all other symptoms reflecting a change in the health situation reported by the participating subjects. Adverse events are sought by non-directive questioning of the patient at each visit during the study, except directive questioning of

symptoms of acute pancreatitis and hypoglycemia. Adverse events also may be detected when they are volunteered by the patient during or between visits or through physical examination, laboratory test, or other assessments. All adverse events, including hypoglycemias, are recorded in the clinical case note and CRF and classified as of mild, moderate or severe degree, and a judgment whether it is related or unrelated to study medication. Hypoglycemia is defined as either a)symptomatic hypoglycemia, b)confirmed hypoglycemia (blood glucose  $\leq 3.1$  mmol/l) or c)hypoglycemia episode that require assistance for control.

The SmPC will be used for Reference Safety Information (RSI) for expected Serious Adverse Events (SAE). These are defined as any untoward medical occurrence that

- Results in death
- Is life threatening (which refers to an event/reaction in which the patient was at risk of death at the time of the event/reaction; it does not refer to an event/reaction which hypothetically might have caused death if it were more severe),
- Requires inpatient hospitalization or results in prolongation of existing hospitalization,
- Results in persistent or significant disability/incapacity, or
- Is a medically important event or reaction.

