## **10. Withdrawal criteria**

A subject may be withdrawn from the trial at the discretion of the Sponsor if judged non-compliant with trial procedures or due to a safety concern.

A subject must be withdrawn if the following applies:

1. **Withdrawal of consent:** The subject may withdraw at will at any time.
2. **Protocol deviation:** If a protocol violation or concurrent illness occurs, which, in the clinical judgement of the Sponsor, may invalidate the trial, the subject will be withdrawn by the Sponsor.
3. **Change in medication:** If a subject changes the dose of their existing medications during the trial, which, in the clinical judgement the Sponsor, may invalidate the trial, the subject will be withdrawn by the Sponsor.
4. **If a subject reports symptoms, which are considered unacceptable by the subject or the Sponsor, such as acute pancreatitis, the subject will be withdrawn from the trial.**

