### **14. Monitoring, data handling and archiving**

The study will be monitored by a certified monitor who is not involved in the study. Study documentation, including informed consent, CRF and laboratory test results, will during the proceeding of the study be kept at the Clinical Research Unit. Sponsor and study nurse will have access to these documents. For statistical analysis, anonymous data file will be created at the Biomedical Center, Lund University. Sponsor will have access to this file. After completion of the study, all documents will be archived at the Biomedical Center at Lund University for 15 years.

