## **17. Study timeline:**

- Q2/2015: Obtaining all permissions and planning of the logistics
- Q3/2015: Screening of patients
- Q4/2015-Q2 2016: Performing the study with FPFV planned for October 2015 and LPFV planned for April 2016
- Q2/2016: Analyses

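### The crossover is analysed with a plain paired test that has no period term, so any period effect shifts the estimate when sequences are unequal and costs power even when they are equal

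*Protocol*

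**What the plan says.** Protocol sections 4 and 8 describe an open-label crossover in which each patient takes both drugs for two weeks, in random order, with a four-week washout between. Each treatment period ends with a meal test. Section 8 says a statistician prepares the randomisation list. It gives no allocation ratio or block size and no statement that the two orders will be equally filled.

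Section 13 has two sentences. The first specifies a two-sided paired test; the second reads "The Completers population alone will be used". The SAP specifies a parametric t-test between the two groups for each hormone. It does not mention pairing, period, sequence or an analysis set.

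Section 12 derives 24 patients for a paired analysis of a 30% glucagon difference with 90% power. To "allow for discontinuation, we will recruit four additional subjects", the target is 28. The SD and the significance level are not given.

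**The concern.** Randomising the order protects a paired comparison from a period effect only on average, or when both orders contribute equally. A period effect here means a difference between the second and first meal test that affects both drugs alike. It could come, for example, from changes in diet or weight during participation, or from assay batch. The documents neither report such an effect nor rule one out.

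Two things follow if one exists. With unequal sequences, part of it enters the drug comparison. With equal sequences it cancels from the mean, but it spreads the within-patient differences, so the paired test treats a systematic component as noise. Inequality can arise from dropout, for which the plan allows four patients, or from the randomisation itself. At stake are the accuracy of the primary glucagon estimate and some of the planned 90% power.

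**Working it through.** **Inputs.** From Protocol section 12: n = 24, power 90%, difference 30%, 28 recruited. From section 13: two-sided paired test. Assumed: 5% level, and period effects π of 5, 10 and 20 points. Points are percentage points of mean glucagon AUC.

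**The plan's own figure.** The 24 cannot be reproduced forwards without an SD. Solving the noncentral-t power equation backwards gives a standardised difference of 0.691, so SD = 30/0.691 = 43.4 points. The standard error at n = 24 is 43.4/√24 = 8.86.

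**Shift.** Let d be vildagliptin minus dapagliflozin within a patient, τ its true mean, and π the second-period minus first-period effect. Patients taking vildagliptin first have mean d of τ − π; those taking dapagliflozin first have τ + π. With n1 and n2 completers in the two orders, the paired mean is off by π(n2−n1)/(n1+n2).
- At 14 versus 10 the fraction is 4/24 = 1/6. The shift is 5/6 = 0.8, 10/6 = 1.7 and 20/6 = 3.3 points.
- At 13 versus 11 it is 2/24 = 1/12, and at 12 versus 12 it is zero.
- Without any dropout, simple randomisation of 28 (an assumption, as the method is not stated) gives a difference of four or more with probability 57%. At 16 versus 12 the fraction is 4/28 = 1/7.

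**Standard error.** The paired test's expected variance of d is SD² + 4·n1·n2·π²/[N(N−1)], with N = n1 + n2. At 12 versus 12 and π = 20 this is 1884 + 400 × 576/552 = 2301. The apparent SD is therefore 48.0 instead of 43.4.

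**Power and type I error.** These come from simulation with at least 100,000 trials per scenario. The rows with π = 0 and the adjusted column agree with exact noncentral-t values. At 14 versus 10 the shift opposes treatment.

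| Completers | π | Shift | Paired power | Period-adjusted power | Paired type I error |
|---|---|---|---|---|---|
| 14/10 | 0 | 0 | 90.0% | 89.1% | 5% |
| 14/10 | 5 | 0.8 | 88% | 89% | 4.9% |
| 14/10 | 10 | 1.7 | 85% | 89% | 4.8% |
| 14/10 | 20 | 3.3 | 76% | 89% | 4.3% |
| 12/12 | 0 | 0 | 90.0% | 89.9% | 5% |
| 12/12 | 20 | 0 | 86% | 90% | 3.2% |

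Hand check of the 76%: the expected estimate is 30 − 3.3 = 26.7. The apparent SD is √(1884 + 400 × 560/552) = 47.9, so the standard error used is 47.9/√24 = 9.77. The critical distance is 2.069 × 9.77 = 20.2, and (26.7 − 20.2)/8.86 = 0.73, or about 77%.

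If the shift instead favours treatment, paired power at 14 versus 10 is about 91–92%, but the estimate is then too large by the same amount.

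**Cost of adjusting.** The variance ratio is N²/(4·n1·n2) = 576/560 = 1.029 at 14 versus 10 and 1 at 12 versus 12. One degree of freedom is also lost.

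**The case against.** The best defence is that this part is small. The largest shift in the table is 3.3 points against a planned 30, it needs both a 20-point period effect and all four losses in one order, and no period effect is documented. If all four losses are random from 14 and 14, the chance that they fall in one order is only 9.8%. The paired test errs on the conservative side, and the two treatment periods use the same meal and the same procedures. All of that stands, and it makes this an improvement rather than a threat to validity. It does not remove the point: dropout is not the only source of imbalance, and the loss of power occurs even with equal sequences.

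A reader might infer something stronger: that an undefined completers set lets patients be dropped after their results are seen. The text gives some reason to ask. Treatment is open ("The study medication will not be blinded"). Where a deviation, illness or dose change, "in the clinical judgement of the Sponsor, may invalidate the trial, the subject will be withdrawn by the Sponsor". The meal-test worksheets go into the CRF, section 14 says "Sponsor and study nurse will have access to these documents", and of the analysis file it says "Sponsor will have access to this file". Deliberately dropping two patients with both results known would raise type I error to about 14%.

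The documents do not support that reading:
- Completing two treatment periods (section 4), the discontinuation allowance (section 12) and the paired test (section 13) together give completer a working meaning: both periods, with both meal tests.
- Section 10 governs withdrawal from the trial, not deletion of a finished patient from the analysis.
- The analysis file is described as anonymous, and the monitor is independent of the study.
- The 28 March 2016 date on both documents falls after the first planned completions but before the planned analysis quarter, so it proves nothing either way.
- The 14% describes misuse that no stated rule produces. Random loss leaves the error at 5%.

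**Conclusion.** The planned analysis should include period. Under the back-calculated SD of 43.4 points and a two-sided 5% level, omitting it moves the estimate by one sixth of any period effect at 14 versus 10 completers: 0.8 to 3.3 points for effects of 5 to 20. If the shift opposes treatment, power falls to between 88% and 76%, where adjustment holds 89%. At 12 versus 12 with a 20-point effect there is no bias, but power is 86% instead of 90%. Type I error stays at or below 5% throughout.

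The period-effect sizes are assumptions. The SD is implied by the plan and not stated in it, and the 14/10 split is the extreme of a 14/14 start that the protocol does not promise. A completers-only analysis is a coherent choice for a mechanistic crossover and is not itself the fault. The remaining gap in its definition, namely which samples make an AUC usable, is a matter of wording.

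**What to change.** Keep completers as the primary set. In Protocol section 13 and the SAP, replace the paired test with a treatment comparison adjusted for period: a linear model with patient, period and treatment. With complete pairs this equals comparing the first-minus-second-period differences between the two sequences and halving the result. Use the same model for the secondary AUCs, and report the number of completers in each sequence.

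As secondary wording:
- State that a completer is a patient with evaluable AUCs in both periods, and which samples make an AUC evaluable.
- Reconcile the AUC window first, because Protocol section 11 uses 180 min, section 12 uses 300 min and the SAP uses 240 min.
- List exclusions by sequence and reason.

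The change needs no new patients or samples. Its price is one degree of freedom plus a variance ratio of 1.03 at 14 versus 10. With no period effect, power falls from 90.0% to 89.1% at 14/10, or to 89.9% at 12/12. The withdrawal rules in section 10 are unaffected.

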### **14. Monitoring, data handling and archiving**

The study will be monitored by a certified monitor who is not involved in the study. Study documentation, including informed consent, CRF and laboratory test results, will during the proceeding of the study be kept at the Clinical Research Unit. Sponsor and study nurse will have access to these documents. For statistical analysis, anonymous data file will be created at the Biomedical Center, Lund University. Sponsor will have access to this file. After completion of the study, all documents will be archived at the Biomedical Center at Lund University for 15 years.

## **15. Risk-benefit analysis**

This is a study aiming at understanding the glucagon response to a mixed meal ingestion after two weeks treatment with the DPP-4 inhibitor vildagliptin and the SGLT2-inhibitor dapagliflozin in patients with metformin-treated type 2 diabetes. Since the study is a mechanistic study, it is of no immediate benefit for the participating patients. The results of the study will, however, be beneficial for the patient group treated with this therapy since it will provide rationale for future treatment by allowing the most pathophysiological treatment to be prescribed to subjects with type 2 diabetes. The risk for the patients participating in the study is minimal since both drugs have been shown to be safe with low risk of adverse events, even in long-term studies, with the exception of genital infections with dapagliflozin. Furthermore, the risk with the mixed meal test is minimal in view of the extensive experience with this test at the Clinical Research Department.

## **16. Insurance**

Insurance is covered by the regular healthy authorities.

## **17. Study timeline:**

- Q2/2015: Obtaining all permissions and planning of the logistics
- Q3/2015: Screening of patients
- Q4/2015-Q2 2016: Performing the study with FPFV planned for October 2015 and LPFV planned for April 2016
- Q2/2016: Analyses

## **18. Publication**

Results will be presented at international meetings and published in international scientific journal.

Statistical analysis plan Protocol 350A

Trial NCT02475070

Study of the Effect of Vildagliptin versus Dapagliflozin on Glucagon

Response to Mixed Meal in Metformin-treated Subjects with Type 2

Diabetes

Glucagon

Comparison between the two groups are performed with parametric t-test for glucagon in samples taken at -5, 15, 30, 45, 60, 90, 120, 180 and 240 min after meal ingestion and area under the 240 min curve (AUC) for glucagon

Insulin, C-peptide, GIP and GLP-1

Comparison between the two groups are performed with parametric t-test for insulin, C-peptide, intact and total GIP and GLP-1 samples taken at -5, 15, 30, 45, 60, 90, 120, 180 and 240 min after meal ingestion and area under the 240 min curve (AUC) for insulin, C-peptide, intact and total GIP and GLP-1.

Lund, March 28, 2016

[name], PI

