## 8. Randomization

Randomization list will be prepared by statistician at Region Skåne and study medication will be distributed to the patient according to the randomization. The study medication will not be blinded and all patients will receive both vildagliptin and dapagliflozin in a cross-over design. The randomization, therefore, is in which order the study medication will be taken.

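### Neither the SAP nor protocol Section 13 adjusts this two-period crossover for period, and the SAP's t-test is not described as paired or two-sided

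*SAP*

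**What the plan says.** Protocol Sections 4 and 7b describe two treatment periods, one drug in each, with meal tests at Weeks 2 and 8. Section 8 states what is randomised: "The randomization, therefore, is in which order the study medication will be taken". It says that "study medication will be distributed to the patient according to the randomization", but gives no allocation ratio and no blocking.

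Section 12 sizes the trial for a paired comparison ("results in requirement of 24 subjects when doing paired analysis") and adds patients to "allow for discontinuation, we will recruit four additional subjects". Section 13 reads "The variables will be analyzed using a 2-sided paired test", followed by "The Completers population alone will be used".

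The SAP describes the test twice: "Comparison between the two groups are performed with parametric t-test for glucagon", and "Comparison between the two groups are performed with parametric t-test for insulin, C-peptide, intact and total GIP and GLP-1". Neither sentence says paired or gives the sidedness. No period or sequence term appears in either document.

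**The concern.** In a two-period crossover each patient's treatment difference also contains the difference between periods, added in one sequence and subtracted in the other. A plain paired test does not separate the two. This has two consequences if glucagon responses drift between Weeks 2 and 8:

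- The period effect adds to the spread of the within-patient differences, so the SD and the confidence interval widen.
- If the sequences contribute unequal numbers of completers, part of the period effect remains in the estimate. Unequal numbers are possible because no ratio or blocking is stated and only completers are analysed.

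Separately, the SAP speaks of two groups and an unqualified t-test in a trial where every patient receives both drugs. Read without the protocol, that could be run as an independent-samples test, which would discard the pairing on which the sample size rests.

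**Working it through.** **Inputs.** From Section 12: a 30% difference, 90% power and 24 subjects, paired. From Section 13: two-sided. Assumed, because not given: alpha 5%; period effects of 5, 10 and 20 points; normal differences. The 30% is treated as 30 percentage points.

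**The plan's own figure.** N = 24 cannot be reproduced, because no SD is stated; it can only be back-solved. By the noncentral t (df 23), 90% power needs a standardised difference of 0.691, so SD = 30/0.691 = 43.4 points. At 28 pairs the same SD gives 94.1%.

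**Formulas.** Let δ be the treatment difference (dapagliflozin minus vildagliptin), π the period effect (period 1 minus period 2), and n1 and n2 the completers receiving dapagliflozin first and second, with N = n1 + n2. Mean within-patient differences are δ + π and δ − π in the two sequences.

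- Plain paired estimate: δ + π(n1 − n2)/N, so the shift is π(n1 − n2)/N.
- SD inflation of the plain test: √[1 + (π²/σ²) × 4n1n2/(N(N − 1))]. At 12/12 and π = 10: √[1 + (100/43.4²) × 576/552] = 1.027. At π = 20: 1.105.
- Adjusted estimate: the average of the two sequence means, with SE = (σ/2)√(1/n1 + 1/n2) and df N − 2.

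**Power at 24 completers.** Adjusted power is exact; plain paired power is by simulation (400,000 data sets per setting). Two values are for the two directions of the period effect.

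| Split | Adjusted | Plain, π = 10 | Plain, π = 20 | Shift at 10 / 20 |
|---|---|---|---|---|
| 12/12 | 89.9% | 89.1% | 85.7% | 0 / 0 |
| 13/11 | 89.7% | 87.3% or 90.5% | 81.3% or 89.4% | 0.8 / 1.7 |
| 14/10 | 89.1% | 85.2% or 92.0% | 76.3% or 92.3% | 1.7 / 3.3 |

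With no period effect the plain test has 90.0% at every split. Adjusted power is 88% at 15/9 and 86% at 16/8. If all 28 complete at 14/14, plain versus adjusted is 93.4% v 94.1% at 10 points and 91.1% v 94.1% at 20.

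**Averaged over splits.** Suppose 14/14 are allocated and four are lost at random; C(28,4) = 20,475. Then 12/12 has probability 91²/20,475 = 0.404, 13/11 either way 2 × 14 × 364/20,475 = 0.498, and 14/10 either way 2 × 1,001/20,475 = 0.098. Weighted over splits and directions, plain versus adjusted power is 90.0% v 89.7% with no period effect, 89.8% v 89.7% at 5 points, 88.9% v 89.7% at 10 and 85.4% v 89.7% at 20. Break-even is at about 5 points.

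**Type I error of the plain test.** For splits from 12/12 to 14/10 it is 3.1% to 5.0%. Conditional on 15/9 it is about 5.3% and 5.9% at 10 and 20 points; conditional on 16/8, about 5.9% and 8.0%. The adjusted test stays at about 5%. Allocation of 14/14 with four losses cannot produce 15/9 or worse. Unblocked 1:1 assignment of 24 patients can: 16/8 or worse has probability 2 × 1,271,626/2^24 = 0.15, and 15/9 or worse 2 × 2,579,130/2^24 = 0.31. Averaged over such a randomisation, the plain test's type I error is 5.0%.

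**If the SAP were run as an independent-samples test** at 24 patients, with assumed within-patient correlations of 0, 0.3, 0.5 and 0.7, power is about 91%, 83%, 71% and 41% and type I error about 5.1%, 2.1%, 0.7% and 0.1%. It would be conservative, and its cost depends on a correlation that the documents do not give.

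**The case against.** The case for leaving the plan alone is substantial. The paired t-test is a legitimate analysis of a crossover, and no document suggests a period effect. The values used here are assumptions, and 20 points is two-thirds of the target difference. On the averages above the plan's test is slightly better with no period effect, about equal at 5 points and less than one point of power worse at 10. Adjustment is also not free: at unequal splits its standard error grows, so it costs most in one of the situations offered as a reason for it. All of that stands and limits the weight of the point. It does not remove the reason to act, because the plain result depends on the unknown size and direction of the period effect and the adjusted one does not. The four-week washout is no answer: it addresses carryover, not period.

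On pairing, a reader might infer that the SAP plans an unpaired analysis. The documents do not support that. Sections 12 and 13 both say paired, the SAP carries the same date as the protocol, nothing says that it overrides Section 13, and an unqualified t-test is silent on pairing and does not contradict it.

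A reader might also infer that the planned test is invalid or inflates false positives. It does not on average over a 1:1 randomisation, nor at splits from 12/12 to 14/10. The excess appears only conditional on a more unequal split together with a sizeable period effect.

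**Conclusion.** Minor. The plan omits a standard adjustment that matches what was randomised, and protocol and SAP describe the test differently. Under the assumptions above, the loss from omitting the adjustment at 12/12 is about 1 point of power at a 10-point period effect and about 4 points at 20. At 13/11 with 20 points, power is 81% or 89% by direction, against 89.7% adjusted. Below about 5 points there is no gain. These figures rest on the back-solved SD, the assumed alpha and illustrative period effects. Nothing here shows that 24 or 28 patients is the wrong number, or that the trial's conclusion would change.

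**What to change.** 1. In both SAP sentences, write *two-sided paired t-test*, in line with Section 13.
2. Add to the SAP and to Section 13, leaving the completers rule in place: *The treatment difference is estimated among completers from within-patient differences adjusted for period (linear model with treatment, period and patient as fixed effects), with a 95% CI and two-sided p-value; this is the primary result, and the unadjusted paired t-test is a check.* For complete pairs this is the same as comparing within-patient period differences between the two sequences.

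This changes the primary analysis of an open-label trial whose timeline (Section 17) places the analyses in Q2 2016, and both documents are dated 28 March 2016. The change should therefore be dated and made before the data are analysed.

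Data collection and sample size are unaffected. The cost is one degree of freedom plus a larger standard error when sequences end unequal. With no period effect, adjusted power is 89.9% at 12/12, 89.7% at 13/11, 89.1% at 14/10, 88% at 15/9 and 86% at 16/8, against 90.0% for the plain test.

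The AUC window, given as 180 min (Section 11), 300 min (Section 12) and 240 min (SAP), is a separate matter that this change neither settles nor endorses.

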### 7b. Methods

A mixed meal will be ingested at Week 2 and Week 8 following. Patients will arrive at the study site in the morning after an overnight fast (from 10 pm). Patients should be instructed to bring their study medication to these visits. Study medication (vildagliptin or dapagliflozin) and the usual morning dose of metformin will be taken 15 minutes

before the start of the standardized mixed breakfast. The start of the meal will be designated time 0 (t = 0 min).

The standardized mixed breakfast meal must be consumed in 15 minutes, and will consist of 524 kcal as rye and wheat bread (67% carbohydrate; 60g), 40% enriched margarine (10g), smoked ham from pork with 3% fat (15g), cheese with 17% fat (15g), juice (285g), green paprika (40g), light sour milk with 0.5% fat (200g) and mix-muesli cereal with fruit (40g) with water and non-sweetened coffee or tea. This breakfast consists of 524 kcal with 60% from carbohydrate, 20% from fat and 20% from protein.

Sampling of blood for determination of plasma levels of glucose, glucagon, insulin, C-peptide, intact and total GLP-1, intact and total GIP will be performed at fixed time points as described in Table 2.

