## **11. End-points**

**Primary end-point** is the effect on the area under the curve (AUC) of the 180 min glucagon levels after mixed meal ingestion

**Secondary end-points** are the effect on AUC180 of GLP-1, GIP, insulin, C-peptide and estimated ISR (insulin secretory rate).

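### The SAP t-tests glucagon at nine time points beside the AUC with no ranking or adjustment: the primary AUC test is unaffected, but claims at single time points have no protection against chance

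*SAP*

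**What the plan says.** Protocol section 11 names one primary end-point, which "is the effect on the area under the curve (AUC) of the 180 min glucagon levels" after the meal. The secondary end-points are 180 min AUCs of the other hormones and an estimated insulin secretory rate. No single time point is listed as an end-point.

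The SAP is organised differently. For glucagon it plans a "parametric t-test for glucagon in samples taken at -5, 15, 30, 45, 60, 90, 120, 180 and 240 min after meal ingestion", joined in one sentence to the "area under the 240 min curve (AUC) for glucagon". For the other hormones it plans a "parametric t-test for insulin, C-peptide, intact and total GIP and GLP-1 samples taken at -5, 15, 30, 45, 60, 90, 120, 180" and 240 min, together with the "area under the 240 min curve (AUC) for insulin, C-peptide, intact and total GIP and GLP-1". Protocol section 7b confirms that intact and total forms are measured for both incretins.

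The SAP does not mark any test as primary, does not call the time points descriptive, and gives no significance level, testing order or multiplicity adjustment. Protocol section 13 adds only that tests are paired and two-sided and use completers.

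**The concern.** The SAP gives ten glucagon tests equal standing: nine time points and one AUC. The objective in Protocol section 3 is broad, asking whether the two drugs have dissociated effects on glucagon after a meal. With no stated ranking, a significant result at one time point could be offered as support for that objective even when the AUC shows nothing, and the plan contains no rule against it. One of the nine samples, at -5 min, is taken before the meal and so cannot show a meal response, yet its test ranks with the rest.

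At stake is the reliability of any statement that glucagon differs between the drugs at a particular time. The validity of the primary AUC test is not at stake.

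**Working it through.** **The plan's own figures.** Neither document gives an error rate for these tests, so there is none to reproduce. The only plan figure used is the sample size in Protocol section 12 (24 for the paired analysis, 28 with the allowance for discontinuation). The 24 cannot be checked because no SD or significance level is given, but the point does not depend on it.

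**Count of tests (SAP; Protocol section 7b).**
- Analytes: glucagon, insulin, C-peptide, intact GIP, total GIP, intact GLP-1, total GLP-1 = 7.
- Tests per analyte: 9 time points + 1 AUC = 10.
- Total: 7 x 10 = 70, made up of 9 glucagon time points, 1 glucagon AUC, 6 x 9 = 54 other time points and 6 other AUCs.

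**Assumptions not in the documents.** Two-sided 5% per test; no true glucagon difference at any time; normally distributed paired differences; a range of correlations between time points.

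**Independent case (upper value).** P(at least one of nine) = 1 - 0.95^9 = 0.37.

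**Equal correlation between all pairs of times.** Simulated paired t-tests, n = 24, 20,000 runs per row. The AUC is trapezoidal over 0 to 240 min, with the -5 min sample as start value.

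| Correlation | At least one time point p<0.05 | Same, with AUC not significant |
|---|---|---|
| 0.95 | 10.0% | 5.0% |
| 0.9 | 13.1% | 8.1% |
| 0.8 | 17.2% | 12.2% |
| 0.7 | 20.7% | 15.8% |
| 0.5 | 27.2% | 22.4% |
| 0.3 | 32.1% | 27.5% |
| 0 | 36.4% | 33.2% |

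The AUC test alone stayed at 4.8% to 5.0% in every row, so the time-point tests do not inflate it. With n = 28 the results barely move: at correlation 0.5, 27.4% and 22.3%.

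**Correlation that fades with time.** Correlation = s + (1 - s) x exp(-lag/tau), with tau from 30 to 240 min and s from 0 to 0.7, n = 24, 10,000 runs per setting. At least one significant time point: 11.3% to 33.2%. The same with the AUC not significant: 6.4% to 29.0%.

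**Combined range, leaving out the independent case.** About 10% to 33% for at least one false-positive time point, and about 5% to 29% with the AUC not significant. The first range does not depend on the AUC window. In the equal-correlation table the second column was computed for 240 min.

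**AUC window across sections.** Protocol section 11: 180 min. Protocol section 12: 300 min. SAP: 240 min. The last sample in Protocol Table 2 is at 240 min, so a 300 min AUC cannot be formed from the planned samples.

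**The case against.** The strongest reply is that the protocol already supplies the hierarchy. It names one primary end-point, sizes the trial on a glucagon AUC and lists no time point as an end-point. On that reading the time points only describe the meal curve, and the study calls itself mechanistic (Protocol section 15). Much of this stands, and it rules out three stronger readings that a reader might infer.

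- **That the trial's primary error rate exceeds 5%.** It does not. Other tests do not change the type I error of a single named AUC test. A higher rate arises only if any time point may also count as proof, and neither document states that rule.
- **That 70 tests imply 70 x 0.05 = 3.5 false positives.** The arithmetic assumes that every comparison is null. Protocol section 6a says vildagliptin raises the active incretins and describes no such action for dapagliflozin, so the 2 x 10 = 20 tests on intact GLP-1 and intact GIP are not expected to be null. Only the nine glucagon time points bear on the glucagon conclusion.
- **That a null AUC with a stray significant time point will be reported as an effect.** That predicts what authors might write. No passage plans it.

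It is also fair that the 5% level and the correlations are assumed, and that the lack of adjustment is inferred from silence.

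The reply does not close the gap. The SAP sets out formal tests at each time point, with no descriptive label and no reference to the protocol's ranking. Its AUC covers a different window from the protocol's primary end-point, so the analysis that should provide the protection is not the one the SAP lists.

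**Conclusion.** The point holds as a limited one. The SAP tests glucagon at nine time points without adjustment and without carrying over the protocol's single primary AUC. The primary test keeps its nominal level once its window is fixed. A claim resting on any one glucagon time point would carry a false-positive chance of about 10% to 33% across the nine points, and about 5% to 29% with the AUC not significant. This rests on an assumed two-sided 5% per test, 24 patients and assumed correlations from very strong to weak. Samples from one meal curve are likely to be correlated, so the 37% for independent tests is an upper value. Even at a correlation of 0.95 the chance is about twice 5%. The change should be made, but the primary comparison does not depend on it.

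**What to change.** 1. Reconcile the glucagon AUC window across Protocol sections 11 and 12 and the SAP, before results are examined. Until this is done there is no defined test to rank first.
2. Name that single AUC in the SAP as the only confirmatory test, at two-sided 5%.
3. Allow claims at glucagon time points only if that AUC is significant, with p-values adjusted across the nine points. A sign-flip max-t permutation, flipping each patient's whole set of paired differences together, makes use of the correlation between times. Holm is simpler and more conservative, with a first threshold of 0.05/9 = 0.0056. With no true difference at any time, the gate holds the chance of any false glucagon claim to 5%.
4. Label the six other AUCs and the 54 other time-point comparisons exploratory, shown as paired mean differences with 95% confidence intervals.

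The cost is a few SAP sentences and a few lines of code, with no extra patients, visits or samples. The downside is fewer nominally significant time points to report, and no time-point claim if the AUC is not significant.
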